1.0 Background & Rationale

Endoscopic resection of large benign lesions is the preferred treatment over surgical resection.

Endoscopic mucosal resection (EMR) is associated with a lower risk and cost compared to surgical treatment. However, it is important that patients undergo endoscopic follow-up after piecemeal EMR in approximately 6 months because there is an approximately 25% risk of recurrence of adenoma polyps ¹.

A randomized controlled trial in only 24 patients showed a significant reduction of the recurrence rate by treatment of the normal appearing perimeter of the EMR defect using the argon plasma coagulator ². A recent non-randomized trial suggested a substantial reduction by treatment of the perimeter with the snare tip in the soft coagulation mode ³.

In this study we are proposing a randomized controlled trial to test Argon Plasma Coagulation (APC) versus Snare Tip Soft Coagulation (STSC) vs no treatment. In a previous trial of APC, the recurrence rate of the control arm was very high at 67%. With only 24 patients in the study the actual benefits of APC remain uncertain. The previous study using STSC was a non-randomized trial. In this trial we hope to provide definitive evidence regarding the efficacy of APC and STSC vs control.

2.0 Objective(s)

2.1 Primary Objective

To investigate the efficacy of APC or STSC in reducing the recurrence rate at the first follow-up after polypectomy of large colon polyps

Hypothesis:

APC or STSC treatment of the perimeter of the EMR defect will reduce the recurrence rate of adenomas when compared to our control of no treatment.

2.2 Secondary Objective

Time it takes to apply each respective treatment (APC or STSC)

Number of complications for each randomization arm. Examples include bleeding, perforation, pain or post polypectomy syndrome.

Cost analysis detailing the effectiveness of the treatment versus the cost of each therapeutic device (argon probe vs. snare).

3.0 Outcome Measures/Endpoints**3.1 Primary Outcome Measures**

Primary outcome is the recurrence rate of adenomas at the site of any qualifying, previously resected lesions at the first follow-up colonoscopy. At the first follow-up the endoscopist will view the polypectomy scar with a high definition colonoscope under white light and NBI for any suspicious polyp tissue. The scar will be biopsied. All polyps noted as recurrent by the endoscopist at colonoscopy and/or by the pathologist based on histopathology will be considered a recurrent polyp.

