5.0 Study Design and procedures

A member of the research team will approach a potential subject to discuss participation in the study, including background of the proposed study, inclusion and exclusion criteria, benefits and risks of the procedures and follow-up. If this is of interest to the subject, the informed consent document will be discussed and presented. The subject must sign the consent form prior to enrollment. This form will have prior approval of the study site's Institutional Review Board (IRB). Failure to obtain informed consent renders the subject ineligible for the study.

Patients who have provided informed consent and are scheduled to undergo endoscopic mucosal resection (EMR) of lesions 15mm and larger will be enrolled in the study. During the procedure randomization will be performed by approved study staff once the colonoscopist confirms the eligibility (at least one sessile polyp greater than 15 mm in the largest dimension measured by the snare size). The three arms of randomization are STSC (80 W, Effect 5) vs APC (preferred settings) vs No Treatment of the perimeter of the EMR site. The randomization list,

which will include 645 randomized treatments, will be generated by our biostatistics department by [name]. These selections will then be printed and placed into sealed envelopes pertaining to the patient numbers and will be opened following confirmation that the patient is study eligible. Randomization will occur on a per procedure basis.

All randomized subjects will receive a 30-day post procedure follow-up phone call (+ 7 days) and be scheduled, as per the standard of care, to receive a standard follow-up colonoscopy procedure after the initial procedure. The follow-up window for the primary endpoint has been extended beyond 6 months due to procedure delays caused by the COVID-19 pandemic. We will measure the rate of recurrence by endoscopic visualization of the EMR site at the first follow-up using endoscopic magnification and electronic chromoendoscopy, as well as systematic biopsy of the scars. Additionally we will look for the presence of scarring and any clips retained.

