6.0 Enrollment/Randomization

All colonoscopies in the study will be performed by [name] or one of the Sub-Investigators listed above. Patients will be 25 and older and will be randomized to one of the aforementioned arms of the study. Blinding of the PI will be maintained until the end of the polypectomy procedure at the primary procedure. Further blinding is not possible due to the nature of the study.

Screen failure: any patient enrolled in the study but not randomized because of not satisfying polyp size or other exclusion criteria discovered during the procedure.

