 - This includes information about the previous EMR site, date of follow-up procedure, pathology results from residual or recurrent polyp tissue found at previous EMR site (if applicable), and pathology results from biopsies obtained from previous EMR site

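### A visual-only call counts as adenoma recurrence even when the biopsy is negative, the follow-up reads are not masked, and no histology-confirmed analysis is pre-specified

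*Combined protocol and SAP*

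**What the plan says.** - **Outcome label.** Section 3.1: "Primary outcome is the recurrence rate of adenomas at the site of any qualifying, previously resected lesions", assessed at the first follow-up colonoscopy.
- **Counting rule.** Section 3.1: "All polyps noted as recurrent by the endoscopist at colonoscopy and/or by the pathologist based on histopathology will be considered a recurrent polyp". No section says what happens when the visual call and the histology disagree.
- **Follow-up assessment.** Section 3.1 specifies a high-definition colonoscope with white light and NBI, and a biopsy of the scar. Section 5.0 adds magnification and electronic chromoendoscopy, "as well as systematic biopsy of the scars".
- **Data collected.** Section 9.0 lists pathology of any residual or recurrent tissue, "and pathology results from biopsies obtained from previous EMR site".
- **Blinding.** Section 6.0: "Blinding of the PI will be maintained until the end of the polypectomy procedure at the primary procedure". It continues: "Further blinding is not possible due to the nature of the study".
- **Who assesses.** Section 6.0 draws every colonoscopist from the PI and the listed sub-investigators ("All colonoscopies in the study will be performed by"), so the follow-up endoscopist may be the index operator.
- **Analysis.** Section 11.0 names chi-square tests for recurrence and one interim analysis. It names no sensitivity or supportive analysis of recurrence.

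**The concern.** The label is histological, but the rule lets one observer's visual judgement create an event that a negative biopsy cannot cancel. That matters most if the observer may know the arm.

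The operator at the index procedure must learn the allocation in order to apply APC, STSC or nothing. The same reasoning does not extend to a pathologist reading biopsies months later. Nor does it extend automatically to the scar assessment, which Section 7.0 places at about Day 180. The plan gives no reason why these two reads could not be masked, wholly or in part.

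False visual calls could move the primary comparison either way. An excess in control scars favours APC and STSC, an excess in treated scars favours control, and equal rates dilute the contrast and cost power. Nothing planned would show readers how far the result rests on visual-only calls. The data for such a display will exist, but an analysis chosen after the arms have been compared carries less weight than one fixed beforehand.

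**Working it through.** **Inputs from Section 11.0.** Recurrence 25% control and 10% in each treated arm; 115 per arm; 80% power; two-sided 5%; final-analysis alpha 0.049.

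**Assumed inputs.** The documents give no false-call rate and no biopsy-miss rate. Let f be the probability that a truly negative scar is called recurrent by eye, and s the probability that biopsy detects a true recurrence. Every true recurrence is taken to be counted in the primary outcome.

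**Step 1: the plan's own figure.** n = [z(α/2)·√(2·0.175·0.825) + z(0.80)·√(0.25·0.75 + 0.10·0.90)]² / 0.15² gives 100 per arm at alpha 0.05 and 101 at 0.049. With continuity correction these become 113 and 114, close to the stated 115. The sample size is not in dispute. Without continuity correction, 115 per arm at alpha 0.049 has 85.2% power, which is the baseline below.

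**Step 2: no true effect, unequal false calls.** The observed rate is 0.25 + 0.75f in each arm. The rejection probability uses the pooled-variance normal approximation, 115 per arm, alpha 0.049.

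| f, control v treated | Observed rates | Type I error |
|---|---|---|
| 0 v 0 | 25.0% v 25.0% | 0.049 |
| 2% v 1% | 26.5% v 25.75% | 0.051 |
| 4% v 2% | 28.0% v 26.5% | 0.056 |
| 5% v 2% | 28.75% v 26.5% | 0.066 |
| 10% v 5% | 32.5% v 28.75% | 0.093 |
| 10% v 2% | 32.5% v 26.5% | 0.167 |

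Swapping the arms gives the same totals, with the excess in favour of control.

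**Step 3: true 25% v 10%, equal false calls.** The observed rates are 0.25 + 0.75f and 0.10 + 0.90f.

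| f | Observed rates | Difference | Power |
|---|---|---|---|
| 0 | 25.0% v 10.0% | 15.0 points | 85.2% |
| 2% | 26.5% v 11.8% | 14.7 points | 81.1% |
| 5% | 28.75% v 14.5% | 14.25 points | 74.7% |
| 10% | 32.5% v 19.0% | 13.5 points | 64.7% |

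**Step 4: what histology alone would give.** With equal s in both arms the rates are 0.25s v 0.10s. At s = 90% that is 22.5% v 9.0%, power 80.4%. At s = 80% it is 20.0% v 8.0%, power 74.7%. The risk ratio stays at 0.40, and the risk difference shrinks to 13.5 or 12 points.

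**Step 5: can the two results together diagnose biased calling?**

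- *Risk ratios (treated/control), true 25% v 10%, equal false calls of 5%.* Primary 0.145/0.2875 = 0.50, histology 0.40, absolute log gap 0.23. There is no differential bias, yet the ratios diverge.
- *Same true rates, false calls 10% control v 2% treated.* Primary 0.118/0.325 = 0.36, histology 0.40, absolute log gap 0.10. There is differential bias, yet the ratios nearly agree.
- *No true effect, 10% v 2%.* Primary 0.265/0.325 = 0.82, histology 1.00, absolute log gap 0.20. In simulation with s = 90% the sampling SD of that gap is 0.14.
- *Discordant count.* Missed biopsies alone, with unbiased assessors, give 115·0.25·(1−s) v 115·0.10·(1−s) visual-positive, histology-negative scars: 2.9 v 1.2 at s = 90%, and 5.8 v 2.3 at s = 80%. A control excess is expected simply because treatment works.

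Neither comparison can serve as a test.

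**The case against.** The best defence is that the either/or rule is sensible. A biopsy can miss recurrence, and a visual call guards against that. Step 4 supports this: histology alone at 80% detection has the same 74.7% power as the planned rule with 5% false calls. The visual call is also made under demanding imaging conditions (Sections 3.1 and 5.0), which argues for low false-call rates. At 2% v 1% or 4% v 2% the type I error barely moves, and at an equal 2% power stays above the planned 80%. The 0.167 figure needs a fivefold difference between arms, for which the documents give no basis. The power loss in Step 3 also disappears if 25% and 10% already describe recurrence as Section 3.1 defines it. All of this stands. It is why the primary definition should not change.

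A reader might go further and infer any of the following, none of which the documents support:

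- **That the assessors are known to be unmasked, or the result biased towards APC and STSC.** Section 6.0 says further blinding is not possible, but no section says whether the follow-up endoscopist or the pathologist knows the arm. Neither the direction nor the size of any bias can be derived.
- **That agreement of the primary and histology risk ratios would clear the trial of biased calling, or disagreement convict it.** Step 5 shows both inferences fail.
- **That the check should count adenoma only.** Sections 4.1 and 4.2 do not restrict the index lesion to adenoma, so that count could drop a confirmed recurrence of another lesion type.

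What the defence does not answer is the blanket blinding sentence and the absence of any planned histology-confirmed result.

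**Conclusion.** The point holds as a gap in bias protection and pre-specification, not as an error in the primary definition or the sample size. A visual-only call is sufficient for an event, the blinding exclusion is wider than its reason, and the collected pathology has no planned use of its own in the recurrence analysis.

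The size is conditional on assumed rates. With no true effect, type I error per comparison lies between 0.051 and 0.167 across the unequal false-call rates shown. With equal false calls of 2% to 10%, power lies between 81% and 65%, provided that 25% v 10% are error-free rates. It is worth acting on because the remedy is cheap and must be settled before the arms are compared.

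**What to change.** Keep the Section 3.1 definition as primary.

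1. **Section 6.0.** Keep the sentence on blinding the PI, and limit the one that follows it to the operator once the perimeter treatment step begins. Add that follow-up scar biopsies go to pathology with no arm on the request form. Where feasible, the follow-up endoscopist should record the scar assessment before consulting the index treatment record. Record whether that endoscopist performed the index procedure.
2. **Section 11.0.** Pre-specify a supportive analysis counting only histologically confirmed recurrent or residual neoplastic polyp tissue at the EMR scar. Show the adenoma-only count as well, and report scars with missing or inadequate biopsy separately. Give risk differences and risk ratios with 95% confidence intervals beside the primary result.
3. **Section 11.0.** Report visual-positive, histology-negative scars by arm as description. State that neither this count nor agreement of the risk ratios is a test for biased calling.

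**Cost.** One supportive analysis and a few table rows from data already collected, one recorded item and a small procedural step at follow-up. No extra patient, biopsy or reader is needed.

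**Limits.** Endoscopist masking is incomplete because the assessor may be the index operator. Masking the pathologist does not affect visual-only calls. The supportive analysis has lower power (about 80% or 75% if biopsy detects 90% or 80% of recurrences, an assumption), so it should not replace the primary.

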3.2 Secondary Outcome Measures

Time it takes to apply each treatment will be recorded by a research assistant during the index procedure using a stop watch. During the colonoscopy the

treatment time will be recorded as the time, after initial polyp resection, that the randomized treatment instrument comes into view until before clips are applied. Complications will be assessed during the follow-up call simply by asking the patients if they experienced any adverse events. We will use the following definitions to ascertain complications:

Bleeding: severe bleeding event that required hospitalization, a blood transfusion, a colonoscopy, surgery, or any other invasive intervention to control bleeding, and that occurred after the patient left the endoscopy unit and within 30 days after completion of the colonoscopy

Perforation: iatrogenic full thickness defect in the colon wall diagnosed within two weeks of the procedure

Pain: Any pain perceived by the patient after they left the endoscopy unit and within 30 days after completion of the colonoscopy

Post polypectomy syndrome: Abdominal pain, fever, leukocytosis and peritoneal inflammation in the absence of perforation within two weeks of the procedure

Our cost analysis will then take all of these endpoints into account to report which method we found to be more affective. As stated, this will be based on the instrument cost, treatment time, polyp recurrence, and reported complications.

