7.0 Study Calendar

Index procedure will be the day of colonoscopy where one of the intervention arms or the control arm is administered. Patients will receive a follow-up phone call at 30-days (+ 7 days) to ascertain any complications as previously described. Patients will also receive a follow-up colonoscopy (standard of care for large polyp removal) where the polypectomy site is observed for any recurrence.

	Index procedure	Follow-up phone call	Follow-up colonoscopy
	Day 1	Day 30 + 7 days	Approximately Day 180
Study Procedures	Colonoscopy with one of the intervention arms or control	Phone call to ascertain complications	Colonoscopy to observe for recurrence at polypectomy site

Lost to follow-up: All patients who are randomized to one of the interventions but fail to complete the required follow-up colonoscopy. Failure to contact at 30 days will not be considered lost to follow-up (complications information in such cases will be deemed acceptable if collected at the first follow-up but an accurate accounting of the number of such patients will be kept and reported to the DSMB).

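### Complications rest on one general question about adverse events, which is likely to miss milder pain and cannot by itself establish post polypectomy syndrome or perforation

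*Combined protocol and SAP*

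**What the plan says.** Section 3.2 sets the method: complications are found at the follow-up call "simply by asking the patients if they experienced any adverse events". Four definitions follow.

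- **Pain** has no severity threshold: "Pain: Any pain perceived by the patient after they left the endoscopy unit and within 30 days after completion of the colonoscopy".
- **Bleeding** counts only if severe enough to need hospital care, transfusion or an invasive intervention, after the patient leaves the unit and within 30 days.
- **Perforation** is a full-thickness defect diagnosed within two weeks.
- **Post polypectomy syndrome** combines pain and fever with leukocytosis and peritoneal inflammation, and requires that perforation be absent.

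Section 7.0 gives the timing: "Patients will receive a follow-up phone call at 30-days (+ 7 days) to ascertain any complications as previously described". If that contact fails, "complications information in such cases will be deemed acceptable if collected at the first follow-up", and "an accurate accounting of the number of such patients will be kept and reported to the DSMB". The study calendar places the follow-up colonoscopy at "Approximately Day 180". Section 5.0 adds: "The follow-up window for the primary endpoint has been extended beyond 6 months". No upper limit is given.

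Section 9.0 lists procedural complications among the index-procedure data. For the call, it lists whether adverse events were reported and, if so, details of them. Section 11.0 compares the number of complications among arms by negative binomial regression.

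**The concern.** The method and the definitions do not match well. Pain is counted at any severity, yet the patient is asked about adverse events, and many would not describe mild discomfort after a colonoscopy in those terms. Leukocytosis, peritoneal inflammation and the exclusion of perforation are clinical findings that a patient cannot supply. The documents describe no item-by-item script, routine record retrieval or adjudication.

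The number of complications in each arm is a stated secondary objective. Two thermal treatments are compared with no treatment, and pain is probably the most frequent of the four events. If pain is captured poorly, a finding of no difference could reflect how the question was put. The same counts enter the cost analysis.

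**Working it through.** **1. Can each defined event be found by the question?**

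| Event | Can the patient report it? | Does the question prompt for it? | Is clinical confirmation needed? |
|---|---|---|---|
| Pain, any severity | Yes | No | No |
| Severe bleeding | Yes, through the care received | No | Useful for dates and intervention |
| Perforation | Only as something the patient was told | No | Yes |
| Post polypectomy syndrome | Pain and fever only | No | Yes |

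**2. Do other provisions close the gap?** The event details in section 9.0 follow a positive answer, so they cannot recover an event the patient did not mention. The procedural complications there come from the index procedure, whereas pain and bleeding are defined as arising after the patient left the unit. The check in section 12.0 verifies 10% of case report forms per site. It tests the accuracy of recorded data and does not search for missed events.

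**3. How late is the fallback?** The 30-day period closes 180 − 30 = 150 days before a day-180 colonoscopy, and longer before a delayed one.

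**4. What does incomplete capture do?** Let p1 and p2 be the true rates and s the fraction captured, equal in both arms, with no false positives.

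- Observed ratio: (s·p1)/(s·p2) = p1/p2, unchanged.
- Observed difference: s·(p1 − p2), reduced in proportion to s.

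**5. Size, on assumed values.** The plan states no figure for complications that could be reproduced. Its only computed size is 115 per arm for recurrence (25% v 10%, 80% power). The continuity-corrected two-proportion formula gives 113 at alpha 0.05 and 114 at 0.049, which agrees closely, and 3 × 115 + 35 = 380. I use n = 115 per arm and a two-sided 5% two-proportion test as a stand-in for the negative binomial model:

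Power = Φ[(d − 1.96·SE0)/SE1], where d = p1 − p2, SE0 = √(2p̄(1 − p̄)/n), SE1 = √(p1(1 − p1)/n + p2(1 − p2)/n), p̄ is the mean of the two rates, and all rates are those observed.

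For assumed true pain of 20% v 8%:

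- s = 1: 20% v 8%, d = 0.12, SE0 = 0.0458, SE1 = 0.0451. The argument is 0.67 and power 75%.
- s = 0.6: 12% v 4.8%, d = 0.072, SE0 = 0.0366, SE1 = 0.0363. The argument is 0.01 and power 50%.
- s = 0.5: 10% v 4%, d = 0.06, SE0 = 0.0337, SE1 = 0.0334. The argument is −0.18 and power 43%.

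The same formula over a range of assumed true rates:

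| True rates | Full capture | 60% capture | 50% capture |
|---|---|---|---|
| 30% v 15% | 78% | 51% | 44% |
| 20% v 8% | 75% | 50% | 43% |
| 10% v 3% | 58% | 38% | 32% |
| 5% v 2% | 23% | 16% | 14% |

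The call covers all randomised patients, 380/3 ≈ 126.7 per arm. With n = 126, the 20% v 8% row becomes 79%, 54% and 46%, so the pattern is the same.

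**6. What if capture differs by arm?** The observed ratio is then (s1/s2) × the true ratio. With assumed capture of 60% in one arm and 50% in the other, a true ratio of 2.5 would appear as 0.6/0.5 × 2.5 = 3.0 or 0.5/0.6 × 2.5 = 2.1, depending on which arm is probed more closely.

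**The case against.** Much can be said for the plan. Pain is defined by the patient's perception, so self-report is its proper source. Severe bleeding is defined by care that a patient can describe and is unlikely to forget by day 30. Perforation would usually lead to care the patient would mention. The call collects details of any reported event, and the definitions are there to classify them. The exact call wording and the case report form are not in the documents, so prompts may exist. These points stand. A reader might infer that the method cannot capture any of the four defined events; the documents do not support that.

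Three other stronger readings also go too far:

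- **Late recall as the general rule.** It is a fallback for patients missed at 30 days, who are counted for the DSMB and might otherwise have no post-discharge complication data. The documents do not say that late answers are pooled with call answers; they are silent on how late data enter the analysis.
- **A certain under-count.** This is likely for milder pain but not demonstrated. Pain with fever and no laboratory result could be misclassified in either direction.
- **Bias toward no difference.** Under the planned model, equal under-capture without false positives leaves the rate ratio unchanged and costs precision. Bias in the ratio needs unequal capture or false positives.

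What the objection does not answer is that an event the patient does not mention goes no further, and that no record confirmation is described for the two events that need it.

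**Conclusion.** The point holds as a weakness in a secondary safety endpoint and in the cost analysis that uses it. The primary endpoint and its sample size are unaffected. The general question is likely to miss milder pain, and it cannot by itself establish post polypectomy syndrome or perforation.

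The fall in power from 75% to 50% or 43% rests on assumed pain rates, assumed equal capture and a simplified test. The documents give no complication rates, no capture fraction and no share of patients missed at 30 days, so the actual loss cannot be computed. Its direction is the same across the rates tried. For rare events (5% v 2%), power is only 23% even with full capture, so better questioning would not make that comparison informative.

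Unequal probing is a separate risk. Section 6.0 keeps the principal investigator blinded until the end of the polypectomy and says further blinding is not possible. The documents do not show that such probing occurs, but an unscripted question leaves room for it.

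**What to change.** At the call already planned, ask one scripted yes/no item for each of: pain, bleeding needing care, hospital or emergency visit, fever, repeat procedure, and perforation. Word the items identically in all arms. After any positive answer, check the site record and classify the event against the section 3.2 definitions.

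In section 11.0, state that the main pain comparison uses call-based data, and show data recalled at the follow-up colonoscopy separately as a sensitivity analysis. The late route can stay for patients not reached at 30 days.

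The cost is a one-page script, a few more minutes per call, and a record check after positive answers. Treatment, visits and sample size do not change. The downside is that reported complication rates will look higher, and patients enrolled before the change need a flag so that the two methods of ascertainment can be told apart.

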8.0 Reportable Events

All adverse events meeting prompt reporting criteria will be reported to the IRB within 5 business days of the study team becoming aware of the event. An adverse event meeting prompt

reporting criteria for this study is defined as any event assessed by the PI, or appropriately trained and qualified designee, as (1) unexpected, (2) related or possibly related to study participation, AND (3) suggesting that the research places subjects or others at greater risk of harm than was previously known. The period for assessing AE's will be from the point of inserting the colonoscope until 30 days after the index colonoscopy.

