11.0 Statistical Considerations

Assuming a 25% recurrence rate of the control arm, and a reduction to 10% in both of the treatment arms, we estimate that a sample size of 115 subjects per arm will be needed to demonstrate that APC and STSC are superior to no treatment for reduction of recurrence rate after EMR, based on 80% power and a two-sided 5% significance level for comparison of independent proportions with one interim analysis. The no treatment arm will be used as our control. In order to account for drop-outs, an extra 35 patients will be enrolled into the study to ensure sufficient data will be included in the analysis. Therefore, a sample size of 380 subjects will be enrolled in this study.

Once a polyp has been identified and its size fits within the targeted range, each subject will be randomized in a 1:1:1 ratio using a computer generated randomization sequence. Enrollment into the study will be competitive with the possibility for each site outside of IU to randomize up to 100 patients. Not all 645 randomization numbers generated will be used in the study. Instead each external site will continue to enroll until a total of 380 patients have been randomized study-wide with a potential to randomize up to 100 patients. Randomization numbers will be assigned as follows: IU will be assigned numbers 001 – 095 and 496 - 526; AdventHealth Orlando will be assigned 096 – 145 and 446 - 470; The Johns Hopkins Hospital will be assigned numbers 146 – 195; Dartmouth-Hitchcock Medical Center will be assigned numbers 196 – 245; NYU Langone Medical Center will assigned numbers 246 – 295 and 471 - 495; the Mount Sinai

Hospital will be assigned 296 – 345, Sibley Memorial Hospital will be assigned 346 – 395, the University of Kansas Medical Center will be assigned 396 – 445, and Penn State Health Milton S. Hershey Medical Center will be assigned 546 - 595. The proportion of subjects with recurrence will be compared between study arms using chi-square tests. The number of complications will be compared among treatment arms using negative binomial regression. Treatment times and costs will be compared between the APC and STSC arms using Wilcoxon Rank Sum tests. A 5% significance level will be used for all tests.

Interim analysis and stopping rule:

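### The pain complication has no body-site or new-onset condition, so unrelated pain counts and can dilute the comparison of complications between arms

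*Combined protocol and SAP*

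**What the plan says.** Section 2.2 makes complications a secondary objective: "Number of complications for each randomization arm. Examples include bleeding, perforation, pain or post polypectomy syndrome". Section 3.2 then defines each one. The pain definition reads "Pain: Any pain perceived by the patient after they left the endoscopy unit and within 30 days after completion of the colonoscopy".

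The neighbouring definitions are narrower. Bleeding must be severe enough to need hospital care, transfusion or an intervention. Perforation is a defect of the colon wall. The fourth names its site: "Post polypectomy syndrome: Abdominal pain, fever, leukocytosis and peritoneal inflammation in the absence of perforation within two weeks of the procedure".

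On collection, Section 3.2 says: "Complications will be assessed during the follow-up call simply by asking the patients if they experienced any adverse events". On analysis, Section 11.0 says: "The number of complications will be compared among treatment arms using negative binomial regression". Complications also enter the cost analysis, since "this will be based on the instrument cost, treatment time, polyp recurrence, and reported complications" (Section 3.2).

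**The concern.** The objective concerns complications by randomised arm, but the scoring rule for pain does not separate procedure-related pain from any other pain in the same month. Three reports show the problem:

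- New abdominal cramping the day after the procedure counts, as intended.
- Long-standing back or knee pain, if the patient mentions it at the call, also counts.
- A headache on day 20 also counts.

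The last two say nothing about treatment of the resection margin, yet the definition does not remove them. Randomisation should make such pain about equally frequent in the three arms, so it does not favour one arm. It adds the same background to each. On a safety comparison, that background makes a finding of no difference more likely if a real difference exists, and it overstates the complication rate in every arm.

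**Working it through.** **Does another section narrow the definition?**

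- Section 8.0 contains a relatedness test ("related or possibly related to study participation"), but it is one of three conditions for prompt reporting to the IRB. It does not govern which pains count under Section 3.2.
- Section 9.0 lists what the external sites transmit. It includes information about any adverse event reported at the call, but no pain status before the procedure.
- Post polypectomy syndrome does not cover isolated abdominal pain, because it also requires fever, leukocytosis and peritoneal inflammation. Abdominal pain alone is therefore counted only under the broad pain definition.

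Nothing narrows it.

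**The plan's own figure.** The only sample-size figure is 115 per arm, for recurrence at 25% v 10% with 80% power (Section 11.0). The continuity-corrected two-proportion formula gives 113 at alpha 0.05 and 114 at 0.049, so the figure reproduces closely. It was not derived for pain and is used below only as a group size.

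**Direction.** Let p be the procedure-related pain rate in an arm and b the rate of unrelated pain, equal in all arms and independent of p. The recorded rate is

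1 − (1 − p)(1 − b).

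For arms with rates p0 and p1, the recorded difference is (p1 − p0)(1 − b). Both the difference and the ratio shrink for any b above 0 when p1 exceeds p0. In a count model the same background adds a mean u to each arm. The ratio (m1 + u)/(m0 + u) is then closer to 1 than m1/m0. The direction therefore does not depend on the assumed rates.

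**Size, as an illustration.** Assumed inputs: p0 = 5%, p1 = 15%, 115 per arm. Power is from exact enumeration of two binomials with an uncorrected chi-square test at two-sided 5%.

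| Unrelated pain b | Recorded control | Recorded treated | Difference (points) | Ratio | Power |
|---|---|---|---|---|---|
| 0 | 5.0% | 15.0% | 10.0 | 3.0 | 74% |
| 5% | 9.75% | 19.25% | 9.5 | 1.97 | 54% |
| 10% | 14.5% | 23.5% | 9.0 | 1.62 | 42% |
| 20% | 24.0% | 32.0% | 8.0 | 1.33 | 27% |
| 30% | 33.5% | 40.5% | 7.0 | 1.21 | 19% |

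Worked example at b = 10%: control 1 − 0.95 × 0.90 = 0.145; treated 1 − 0.85 × 0.90 = 0.235; ratio 0.235/0.145 = 1.62.

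With 10% v 20% instead, power is 57% at b = 0, 37% at b = 10% and 26% at b = 20%. A normal-approximation formula gives slightly lower power for 5% v 15% (72% at b = 0, 41% at b = 10%) and the same pattern.

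**The case against.** **Only volunteered pain is recorded.** Patients are asked an open question about adverse events, and many would not mention chronic knee pain in reply. This stands. It probably keeps b low, so the 20% and 30% rows should carry little weight. It does not repair the definition, because what counts is then left to what each patient happens to mention.

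**The calculation is not the planned test.** The plan specifies negative binomial regression on the number of complications across three arms, not a two-arm chi-square on pain. It claims no power for complications. Patients who miss the follow-up colonoscopy can still contribute to the 30-day data, so the group could approach 380/3, about 127. This stands too: the power figures are illustrative, and the effect on the planned analysis has not been computed.

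**The absolute excess barely moves.** It falls only from 10.0 to 9.5 or 9.0 points at b = 5% or 10%. That is correct. Most of the loss comes from the higher background, which lowers the ratio and adds variance.

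**A broad, patient-perceived definition is defensible.** Blinding ends with the polypectomy (Section 6.0), and counting all pain requires no judgement from a caller who may know the arm. This argues against a relatedness judgement. It argues less strongly against body site and onset, which the patient can state.

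**Details of the event are already collected.** Where location is noted, abdominal pain could be tabulated separately. But the plan does not require location to be recorded or such a table to be produced.

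A reader might infer that the definition does hide a real excess of abdominal pain after APC or STSC. The documents do not support that. They give no pain rates by arm and no evidence that an excess exists.

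**Conclusion.** The point holds as a minor one. Section 3.2 states a rule that counts pain of any site and any onset, and no other section restricts it. Unrelated pain that patients volunteer can dilute a difference in procedure-related pain and in the complication count, and it overstates the complication rate in every arm.

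The direction follows from the arithmetic, given unrelated pain that is equal across arms. The size does not: it rests on assumed pain rates, on an assumed 5% to 10% of patients reporting unrelated pain, and on a yes/no test standing in for the planned count model.

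The reach is limited to one component of a secondary endpoint and the cost analysis it feeds. The primary endpoint, the sample size and the interim rule are unaffected.

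**What to change.** Keep the present time window in Section 3.2, including its start at departure from the endoscopy unit, and narrow which pain counts. For example: *Pain: abdominal or anorectal pain that the patient reports as new, or as worse than before the index colonoscopy, within the existing post-discharge window to 30 days.* The start of the window matters. Dropping it would bring recovery-room cramping into the count in every arm and reintroduce background of the same kind.

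Add two items, body site and new-or-worse, to the adverse event details already taken at the 30-day call. List pain at other sites as adverse events outside the complication count, so that no safety information is lost. Base the classification on site and onset as the patient states them, not on the caller's view of relatedness.

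The cost is one line of protocol text and two data items. There are three small downsides: fewer pain events will be counted, a rare referred pain at another site will be missed, and the answer on worsening will rest on recall at about 30 days, since Section 9.0 lists no baseline pain.
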